### Figure 5 Part 2 Dose Escalation for Maintenance Dosing MTD and Expansion

Each part of the study includes a screening period, a treatment period, and a follow up period. Participants will be screened for eligibility beginning 4 weeks (or 28 days) before the start of treatment.

### **Dose Escalation**

To complete dose escalation in Part 1, it is estimated that up to 22 participants will be enrolled. Dose escalation for Part 1 will use the N-CRM. This method utilizes a 2parameter logistic model, with parameters  $\alpha$  and  $\beta$ , to describe the relationship between DLT and dose (12.5, 25, 50, 100, 200 µg). The N-CRM estimates, for each potential dose, the posterior probabilities that the DLT rate lies in each of 4 toxicity intervals:

- [0%,16%)=Underdosing range;
- [16%,33%)=Target toxicity range;
- [33%,50%)=Excessive toxicity range;
- [50%,100%)=Unacceptable toxicity range.

Additionally, the following constraints for the recommended dose will be maintained:

The posterior probability of the DLT rate lying in the Excessive Toxicity or Unacceptable Toxicity range is less than 25%.

Dose escalation will continue until:

i. An MTD is found:

At least 9 participants have been treated at the current target dose

AND

The posterior probability that the DLT rate for the current dose lies in either the excessive toxicity or unacceptable toxicity range is less than 25%.

AND

The posterior probability that the DLT rate for the next higher dose lies in either the excessive toxicity or unacceptable toxicity range is greater than or equal to 25%.

OR

ii. The RP2D has been reached and at least 9 participants have been dosed at that dose level.

OR

iii. All doses have a posterior probability of lying in either the excessive toxicity or unacceptable toxicity range of greater than or equal to 25%

AND

At least 2 DLTs have been observed.

All available data, including safety, PK, and pharmacodynamic data from current and prior cohorts will be reviewed at dose escalation meetings after each cohort in Part 1. Clinical judgment by the Medical Monitor, recommendation from GSK clinical pharmacologist, GSK scientist and GSK statistician, and in consultation with the investigators can decide dose escalation or reduce the recommended dose as deemed appropriate at any time during the trial.

**Maximum Tolerated Dose:** The MTD will be defined as the dose within cycle that has the highest probability of having a DLT rate within the target toxicity interval, and for which the probability that the DLT rate lies within the excessive toxicity, or the unacceptable toxicity window is less than 25%. The DLT observation period will be 28 days.

**Recommended Phase 2 Dose:** RP2D of GSK3745417 will be determined after review of all available safety, PK, pharmacodynamics, and clinical efficacy data. The RP2D will be equivalent with the MTD or a lower GSK3745417 dose and regimen that provides adequate PK exposure and biologic activity with acceptable safety and tolerability.

Maintenance dose escalation for Part 2 will use the mTPI method as described in Section 9.2. Dose escalation will proceed until the MTD for GSK3745417 for a specific maintenance dosing schedule is determined.

# 4.1.1. Dose Limiting Toxicities (DLT)

All toxicities will be graded using National Cancer Institute – Common Toxicity Criteria for AEs (NCI-CTCAE), version 5.0.

An AE is considered to be a DLT if it is considered by the investigator to be clinically relevant and attributed (definitely, probably, or possibly) to the study intervention and meets at least 1 of the criteria listed in the table below. If an AE is considered related to the underlying disease it is not a DLT. The DLT period is 28 -days starting at Day 1 of each cycle. Participants unable to receive at least 70% of scheduled doses within the DLT

period for reasons other than toxicity (e.g., acute illness, disease progression) will not be considered evaluable.

Toxicity	DLT Definition			
Cytokine Release Syndrome (CRS)	Grade 3 or 4 (See Section 10.4)			
TLS	Grade 3 or Grade 4 TLS (Cairo Bishop criteria, Appendix 11) that cannot be managed/ is not resolved within 72 hours			
Liver Toxicity	ALT $\geq$ 3x upper limit of normal (ULN), plus bilirubin $\geq$ 2x ULN (>35% direct) or plus international normalized ratio (INR)>1.5 (Possible Hy's law)			
Other	
 
Grade ≥3 non-hematologic toxicity of any duration with the following exceptions:
 
Transient (≤ 72 hours) abnormal laboratory value without associated clinically significant signs or symptoms
 
Individual parameters of CRS which collectively constitute <grade 3="" crs<="" li=""> 
Nausea, vomiting, or diarrhea that improves with supportive care within 72 hours
 
Alopecia of any grade
 
Grade 3 fatigue with duration <7 days
 
Grade 3 headache that resolves with supportive treatment to ≤Grade 2 within 24 hours
 
G3 acute renal injury considered related to TLS which improves or resolves with appropriate fluids and management of TLS
 
Grade ≥3 immune-related toxicity that does not resolve to Grade ≤1 or baseline within 8 days despite adequate immune suppressive therapy. Any other event which in the judgment of the investigator and GSK Medical Monitor is considered to be a DLT.
 </grade>

			

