# CONFIDENTIAL

DE Cohort	Screeningª	Cycle (Induction Period)			Follov (post-fin adminis	w-Up al dose stered)	
Study Procedure		Intervent (In-P	tion Period atient)	Observation Period (Outpatient)	TDV⁵	Follow- Up	Notes
Week	≤4	1	- 2	3 - 4	+4		
Day	≤28	-1	1 - 13	14 - 28	+30d		
Urinalysis⁰	x		Х		Х		Sample collection times: Days 1, 8 and 13 of each cycle. If urinalysis is abnormal, a microscopy should be performed.
Coagulation	x		х				Sample collection times: at screening and prior to administration of first dose of GSK3745417 and at Day 8 of each cycle. Additional coagulation samples should be collected in the event of CRS (see Section 6.4.1.4)
Study Intervention	•						· · ·
Administer GSK3745417			X				GSK3745417 will be administered the same dose within each cycle on Days 1 – 5 and Days 8 - 12 QD. Participants will receive up to 3 cycles of treatment before moving to Q1W or Q3W dosing (Section 6.1). See Section 4.1 for maximum duration of study intervention. See Section 4.1 for safety and tolerability parameters to be reviewed prior to each daily dose
Non-Azole Antifungal		х	Х	Х			Non-azole antifungals should be administered if indicated, per local standard, on Day -1 through Day 28 of each cycle.
Tumor Lysis Syndrome Prophylaxis		x					All participants should receive tumor lysis syndrome (TLS) prophylaxis prior to date of first dose of each cycle on Day -1 according to institutional guidelines (e.g., participants should receive IV fluids ± allopurinol and consider alkalization of urine and

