### Table 7Dose-Limiting Toxicities

Participants who withdraw from the study before completing DLT period for reasons other than DLT may be replaced. If a participant experiences a DLT during the DLT period of treatment, the participant will be discontinued from study treatment unless the investigator considers it in the best interest of the participant to continue on study (e.g., in case of symptomatic disease improvement, and/or if the DLT is viewed as preventable in subsequent doses/visits, etc.) and the sponsor approves of the decision.

Guidance for the management of toxicity, including dose modification algorithms, is provided in Section 6.4.

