# 5.1. Inclusion Criteria

Participants are eligible for inclusion in this study if all the following criteria apply:

1. Must be  $\geq 18$  years of age and  $\leq 75$  years of age at the time of signing the informed consent for dose escalation and  $\geq 18$  years of age at the time of signing the informed consent for the dose expansion.

- 2. Capable of giving signed informed consent which includes compliance with the requirements and restrictions listed in the informed consent form (ICF) and in the protocol.
- 3. Eastern Cooperative Oncology Group (ECOG) performance status of 0 or 1.
- 4. Participants with AML/High Risk MDS are eligible for participation in Part 1 and Part 2 if they have:
  - A diagnosis of AML according to the World Health Organization 2016 criteria (Arber, 2016) with relapsed or refractory disease and ineligible for or have exhausted standard therapeutic options.
  - Have high-risk or high/very high by IPSS-Revised [IPSS-R] criteria [Greenberg] MDS (restricted to Part 1) that has relapsed after or been refractory to prior therapy with hypomethylating agent.

5.	Adeq	uate	organ	function:	
----	------	------	-------	-----------	--

Organ system	Laboratory Values	
Hematologic		
White blood cell count (absolute)	≤25,000/µL (both at screening and prior to study drug administration on Day 1) (hydroxyurea is permitted to reduce white cell count prior to screening). Hydroxyurea or leukapheresis may be used prior to and throughout study to control white cell count	
PT/INR and PTT in patients not receiving therapeutic anticoagulants	≤1.5 x ULN	
PT/INR and PTT in patients receiving therapeutic	Within the intended therapeutic range of the	
anticoagulants	anticoagulant	
Hepatic		
Total bilirubin	≤1.5 x ULN	
For participants with Gilbert's Syndrome (only if	$\leq 3.0 \times ULN$	
direct bilirubin 🛛 35%)		
ALT	≤2.5 x ULN	
Renal		
eGFR by CKD-EPI	≥50mL/min/1.73m 	
Endocrine		
TSH 	WNL	
Cardiac		
Ejection fraction	≥Lower limit of normal (LLN) (minimum of 50%)	

 If TSH is not within normal limits at baseline, the participant may still be eligible if total T3 or free T3 and free T4 are within the normal limits

6. Participants with a prior history of stem cell transplant (autologous and/or allogeneic) are allowed if:

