# 6.7. Concomitant Therapy

# 6.7.1. Permitted Medications

Participants considered to have an increased risk of thrombosis (e.g., history of catheter related clots, DVT) can be considered for prophylactic anticoagulation per local practice and/or clinical judgement.

Prophylaxis for CRS is not mandated. However, if a participant has CRS, prophylaxis with antihistamines and paracetamol /acetaminophen is permitted on subsequent infusions. NSAIDs for fever or symptoms control should be avoided due to risk of renal injury.

Participants receiving hormonal therapy for a definitively treated malignancy (e.g., adjuvant therapy of localized breast or prostate cancer) may continue to receive therapy during study, after discussion with the medical monitor.

Erythropoiesis-stimulating agents and colony-stimulating factors like filgrastim and pegfilgrastim may be used as clinically indicated for treatment of cytopenias. If used, these agents should be held for a period prior to disease assessment, per local institutional practice or guidelines.

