## Events Meeting the AE Definition

- Any abnormal laboratory test results (hematology, clinical chemistry, or urinalysis) or other safety assessments (e.g., ECG, radiological scans, vital signs measurements), including those that worsen from baseline, considered clinically significant in the medical and scientific judgment of the investigator (i.e., not related to progression of underlying disease).
- Exacerbation of a chronic or intermittent pre-existing condition including either an increase in frequency and/or intensity of the condition.

- New conditions detected or diagnosed after study intervention administration even though it may have been present before the start of the study.
- Signs, symptoms, or the clinical sequelae of a suspected intervention- intervention interaction.
- Signs, symptoms, or the clinical sequelae of a suspected overdose of either study intervention or a concomitant medication. Overdose per se will not be reported as an AE/SAE unless it is an intentional overdose taken with possible suicidal/self-harming intent. Such overdoses should be reported regardless of sequelae.
- "Lack of efficacy" or "failure of expected pharmacological action" per se will not be reported as an AE or SAE. Such instances will be captured in the efficacy assessments. However, the signs, symptoms, and/or clinical sequelae resulting from lack of efficacy will be reported as AE or SAE if they fulfill the definition of an AE or SAE.

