## 10.7. Appendix 7: Liver Safety: Required Actions and Follow-up Assessments and Study Intervention Restart/Rechallenge Guidelines

- http://www.fda.gov/downloads/Drugs/GuidanceComplianceRegulatoryInformation/G uidances/UCM174090.pdf
- http://www.fda.gov/downloads/Drugs/GuidanceComplianceRegulatoryInformation/G uidances/UCM174090.pdfhttp://www.fda.gov/downloads/Drugs/GuidanceComplianc eRegulatoryInformation/Guidances/UCM174090.pdf
  - http://www.fda.gov/downloads/Drugs/GuidanceComplianceRegulatoryInformatio n/Guidances/UCM174090.pdf
  - https://doi.org/10.1016/j.jhep.2019.02.014

Phase 1 oncology liver chemistry stopping criteria have been designed to assure participant safety and to evaluate liver event etiology.

Liv	Liver Chemistry Stopping Criteria – Liver Stopping Event				
ALT absolute	Both ALT $\geq$ 5xULN and $\geq$ 2x	Both ALT $\geq$ 5xULN and $\geq$ 2x baseline value			
ALT Increase	Both ALT $\geq$ 3xULN and $\geq$ 1.	5x baseline value that persists for $\geq$ 4 weeks			
Bilirubin 	ALT $\geq$ 3xULN and bilirubin $\geq$	2xULN (>35% direct bilirubin)			
INR 	ALT $\ge$ 3xULN and INR>1.5				
Cannot Monitor	Both ALT $\geq$ 3xULN and $\geq$ 1.	5x baseline value that cannot be monitored for			
	4 weeks				
Symptomatic 	Both ALT $\geq$ 3xULN and $\geq$ 1.	5x baseline value associated with symptoms (new			
	or worsening) believed to be	related to liver injury or hypersensitivity			
Required Action	s and Follow up Assessme	ents following ANY Liver Stopping Event			
A	Actions	Follow Up Assessments			

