
 
perform liver event follow up assessments within 24 hr
 
Monitor participants twice weekly until liver chemistries resolve, stabilize, or return to within baseline
 
A specialist or hepatology consultation is recommended
 
For All other criteria:
 
Repeat liver chemistries (include ALT, AST, alkaline phosphatase, bilirubin and INR) and perform liver event follow up assessments within 24-72 hr
 
Monitor participants weekly until liver chemistries resolve, stabilize, or return to within baseline
 
	
 
For bilirubin or INR criteria:
 
Anti-nuclear antibody, anti-smooth muscle antibody, Type 1 anti-liver kidney microsomal antibodies, and quantitative total immunoglobulin G (IgG or gamma globulins)
 
Serum acetaminophen adduct HPLC assay (quantifies potential acetaminophen contribution to liver injury in participants with definite or likely acetaminophen use in the preceding week [James, 2009]). NOTE: not required in China
 
Liver imaging (ultrasound, magnetic resonance, or computerized tomography) and /or liver biopsy to evaluate liver disease complete Liver Imaging and/or Liver Biopsy CRF forms
 

 
Serum bilirubin fractionation should be performed if testi immediately available, discontinue study treatment for th Additionally, if serum bilirubin fractionation testing is una
 
	ng is available. If serum bilirubin fractionation is not at participant if ALT $\geq$ 3xULN and bilirubin $\geq$ 2xULN. available, record presence of detectable urinary bilirubin on

dipstick, indicating direct bilirubin elevations and suggesting liver injury.
All events of ALT ≥ 3xULN and bilirubin ≥ 2xULN (>35% direct bilirubin) or ALT ≥ 3xULN and INR>1.5, which may indicate severe liver injury (possible 'Hy's Law'), must be reported as an SAE (excluding studies of hepatic impairment or cirrhosis); the threshold value stated will not apply to participants receiving anticoagulants

- New or worsening symptoms believed to be related to liver injury (such as fatigue, nausea, vomiting, right upper quadrant pain or tenderness, or jaundice) or believed to be related to hypersensitivity (such as fever, rash, or eosinophilia)

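### Table 7's liver DLT counts INR above 1.5 without the anticoagulant exception that Appendix 7 attaches to the same ALT/INR threshold, although criterion 5 admits anticoagulated participants

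*Protocol*

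**What the plan says.** **DLT definition.** Protocol Section 4.1.1, Table 7, has one liver row. It is met by ALT ≥3xULN together with either bilirubin ≥2xULN (more than 35% direct) "or plus international normalized ratio (INR)>1.5 (Possible Hy's law"). The row does not mention anticoagulants. SAP Section 4.2.1 takes the DLT criteria from Table 7 and adds nothing to them.

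**Stopping and SAE rules.** The liver stopping table in Protocol Appendix 7 (Section 10.7) has an INR row with the same pair, ALT ≥"3xULN and INR>1.5". That row is marked with footnote 2, which also calls the pair possible Hy's law and ends: "the threshold value stated will not apply to participants receiving anticoagulants". Section 10.3.2 g and the note to Table 16 (Section 10.2) give the pair again as an SAE trigger, without the exception.

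**Who can be enrolled.** Criterion 5 (Section 5.1) gives participants on therapeutic anticoagulants their own PT/INR row. The requirement is "Within the intended therapeutic range of the" anticoagulant. ALT may be up to 2.5xULN at entry. Section 6.7.1 adds that participants at raised risk of thrombosis "can be considered for prophylactic anticoagulation per local practice and/or clinical judgement".

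**When INR is measured.** The coagulation row of the Part 1 schedule (Table 1) reads "Sample collection times: at screening and prior to administration of first dose of GSK3745417 and at Day 8 of each cycle". At least one scheduled on-treatment INR therefore falls inside the 28-day DLT window.

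**Consequence for the participant.** After a DLT, "the participant will be discontinued from study treatment unless the investigator considers it in the best interest of the participant to continue on study" and the sponsor agrees.

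**The concern.** An INR above 1.5 helps to identify severe liver injury because it points to failing synthesis of clotting factors. In a participant whose anticoagulant raises INR, the value is explained by the treatment and says little about the liver. Footnote 2 shows that the protocol recognises this for stopping and SAE reporting. The DLT row does not carry it over.

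For such a participant the INR half of the criterion can be met before the first dose. What remains is the ALT half, and entry is allowed at up to 2.5xULN. A moderate ALT elevation that would otherwise not be a DLT can then be scored as possible Hy's law.

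DLT is part of the primary endpoint of Part 1 and the input to the N-CRM. A scored DLT also leads by default to discontinuation and bars the participant from intra-patient escalation (Sections 4.1.2 and 6.4.1.1).

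**Working it through.** **1. The same values under each rule.** Take an anticoagulated participant with ALT at or just above 3xULN judged related to study drug, bilirubin below 2xULN, INR above 1.5 because of the anticoagulant, and no other Table 7 criterion met.

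- Table 7, bilirubin limb: not met.
- Table 7, INR limb: met, so a DLT.
- Appendix 7, INR row: disapplied by footnote 2. Other Appendix 7 rows may still apply, depending on the size and persistence of the ALT rise.
- Section 10.3.2 g and Table 16 note: met as written, so an SAE, although footnote 2 takes the same case out of SAE reporting.

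The documents give no therapeutic INR range. A range of 2 to 3 is an assumption, and any value above 1.5 gives the same result. An anticoagulant that leaves INR at or below 1.5 has no effect on this point.

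**2. ALT rise needed to reach 3xULN.**

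- From the entry ceiling: 3.0/2.5 = 1.20, a 20% rise.
- From 1.0xULN: 3.0/1.0 = 3.00, a 200% rise.

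**3. Effect of one DLT on escalation.** There is no stated figure to reproduce for this point. Inputs are from Protocol Section 9.2: logit p = α + β·ln(dose/50 µg), with (α, ln β) bivariate normal, means −1.7907 and 0.1961, SDs 1.6787 and 0.1706, correlation −0.7729, and doses 12.5, 25, 50, 100 and 200 µg. Section 4.1 requires P(DLT rate ≥33%) below 25% for a recommended dose. The posterior was obtained by grid integration with all lower cohorts at 0/3. P(DLT rate ≥33%) at the **next** dose is:

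| Step | 0/3 | 1/3 | 1/6 | 1/9 |
|---|---|---|---|---|
| 12.5 to 25 µg | 4.9% | 37.9% | 19.6% | 10.3% |
| 25 to 50 µg | 6.6% | 35.8% | 20.7% | 11.9% |
| 50 to 100 µg | 11.6% | 43.1% | 27.4% | 17.2% |
| 100 to 200 µg | 22.5% | 56.9% | 40.2% | 27.6% |

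At the **current** dose after 1/3 the same probability is 17.2%, 11.6%, 12.6% and 17.5% for the four rows. All are below 25%, so the model holds the dose and does not de-escalate.

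At the lower two steps the hold lifts at 1/6, and at 50 µg it lifts at 1/9. At 100 µg it has not lifted by 1/9. There, 1/9 gives 2.5% at the current dose and 27.6% at the next, which meets stopping rule (i). With 0/9 the figures are 0.3% and 8.1%, and the rule is not met.

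These figures show what **any** single DLT does. They do not measure how often the INR case occurs. That would need the number of anticoagulated participants, the agents they take and their rate of ALT elevation, none of which the documents give.

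**The case against.** **Judgment already filters these events.** Section 4.1.1 requires the investigator to find the event clinically relevant and attributable to study drug. An abnormal laboratory result is an AE only if "considered clinically significant in the medical and scientific judgment of the investigator" (Section 10.3.1). The causality text in Section 10.3.4 tells the investigator to weigh concomitant therapy as an alternative cause. This has real force, and it defeats the stronger reading that every anticoagulated participant whose ALT reaches 3xULN is automatically a DLT. It does not close the gap. When the ALT rise is itself judged drug-related, the event passes the gate properly, and Table 7 then classifies it with no instruction on how to treat the INR. Table 7 does not rely on judgment alone elsewhere: it writes out exceptions for transient laboratory values, components of CRS and TLS-related renal injury.

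**Footnote 2 is not about DLTs.** It is written for SAE reporting and marks liver stopping rows. A reader might infer that the protocol holds two contradictory DLT rules. It does not, because only Table 7 defines a DLT, and a DLT rule may be stricter than a stopping rule. What stands is that the same threshold, with the same Hy's-law label, is disapplied for this group in one place and used unqualified in another, with no reason given.

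**Section 6.7.1 is weak support.** It covers prophylactic anticoagulation only, and nothing in the documents says that this raises INR. The point rests on criterion 5.

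**The error is on the safe side.** A false DLT pauses escalation. The dose escalation committee reviews all safety data and may apply clinical judgment before acting. Both are correct, and they limit the weight of the point.

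**Conclusion.** The point holds as a limited gap in the DLT definition, worth correcting but minor. As written, Table 7 can score a DLT on an INR that the anticoagulant explains. This requires an anticoagulant that raises INR above 1.5, ALT ≥3xULN attributed to study drug, bilirubin below 2xULN, no other Table 7 criterion met, and an investigator who reads the INR limb literally.

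The frequency is unknown. If it occurs, the effect is that of any one DLT in a cohort of three: the next dose crosses the 25% limit at every step and escalation is held, in the conservative direction. This rests on the stated prior, the 50 µg reference dose and clean lower cohorts.

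A reader might infer that the Part 1 escalation or its MTD was distorted. The documents do not support this, since nothing in them shows that such an event occurred. SAP Section 4.8 records that the study was terminated just as Part 1 finished recruiting, so what remains for this study is how DLTs are reported.

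**What to change.** **Protocol wording.** Qualify the INR limb of Table 7 so that INR >1.5 does not count for participants receiving anticoagulants, as in footnote 2. Their liver events would then be scored through the bilirubin limb, the Grade ≥3 non-hematologic clause or the investigator/Medical Monitor judgment clause. Make Section 10.3.2 g and the Table 16 note agree with footnote 2. With recruitment over, this cannot change a dosing decision in this study; its value is consistency within the protocol and in any later protocol that reuses the table.

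**SAP.** Do not add the exception to Section 4.2.1 or reclassify any DLT. Changing a primary endpoint after recruitment in an open-label study would make the reported DLTs differ from those the investigators scored and the N-CRM used. Keep them as scored, and flag in the DLT listing any liver DLT met solely through INR in an anticoagulated participant. A reader could assemble this from the AE and concomitant medication listings together with the INR results, but the flag makes it visible.

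**Cost.** One qualifier in Table 7, matching wording in two other places and one listing flag, using INR and concomitant medication data already collected. The downside is that a true INR rise in an anticoagulated participant is no longer scored automatically and depends on the other clauses. A rule based on change from baseline INR would keep that signal, but it needs a clinically chosen threshold that the documents do not supply.
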